6.5. Screening failure

Subjects that have signed the Informed Consent Form but fails to comply with inclusion or exclusion criteria are considered screening failures. A screening failure can be replaced by a new subject if the subject can complete the investigation within timelines (before last subject last visit and within visit windows).

6.6. Point of enrolment

A subject is considered enrolled in the investigation when the written informed consent is obtained. The expected duration for each subject is described in section 5.1.

6.7. Subject Identification and Confidentiality

Subjects will be identified on the electronic CRF (e-CRF), and any other document transmitted to the sponsor by the principal investigator or delegate, by a unique identification number.

Data entered on the e-CRF are confidential and will only be available to the sponsor (including sponsor delegates), members of data management teams, the statistician, data monitoring board members or clinical event committee members if involved, members of the EC and if requested to regulatory authorities.

The principal investigator for each clinical investigation site will maintain as part of the investigational file a list identifying all subjects entered into the clinical investigation.

7. Procedures

7.1. Clinical investigation related procedures and assessments

Visit 0 (V0) Screening visit

- Introduction to the investigation and review of Participant Information Sheet and Informed Consent Form
- Review in- and exclusion criteria
- Schedule Baseline visit (V1) within 72 hours since injury, unless performed at the same day as Screening visit V0
- Register the potential subject on the Pre-screenings log.

Baseline visit (V1)

- Review Participant information Sheet and Informed Consent Form
- Check in- and exclusion criteria
- Informed Consent signed
- Inclusion in the study and allocation of subject number
- Collect baseline information:
 - Age (years)
 - Weight (kg)
 - Height (cm)
 - Gender (male/female)
 - Nutritional status (well-nourished, malnourished)
 - Mobility status (good mobility, bad mobility)
 - Smoking (yes/no)
 - Alcohol (Units/week)
 - Comorbidities (That can affect wound healing (diabetes, venous insufficiency, peripheral arterial disease, cardiopulmonary conditions, immune deficiencies, dementia, other) or none as deemed relevant by investigator)

- Relevant concomitant medication (that can impact wound healing e.g., NSAID, Glucocorticoid steroids and chemotherapeutic drugs)
- Use of antiseptics in study wound within the last week (yes/no) and reason for use.
- Cleansing of wound according to standard of care (record product applied)
- Photo of wound and upload to a digital [REDACTED]

Wound description/assessment

- Reason of burn (thermal, Chemical, other)
- Duration of wound
- Previous wound treatment/treatment at time of inclusion (if applicable)
- Wound size (measured by photo uploaded to a digital [REDACTED])
- Wound location (upper extremity, lower extremity- leg, lower extremity-foot, abdomen, thorax, back, buttock/sacrum, other)
- [REDACTED]
- [REDACTED]
- [REDACTED]
- [REDACTED]
- Dressing application according to IFU
- Record applied additional relevant wound care products (e.g., secondary dressing or barrier cream)
- Instruction to the subject (including sheet for dressing change between scheduled visits)
- Scheduling Visit 2 in Week 1, 7 days (+/-2 days) after Visit 1 (Attention to compliance with maximum wear time of 7 days according to IFU)
- Complete eCRF
- Perform device accountability

Visit 2 (V2)

- Insurance of subject's wellbeing. Review of AEs/ADEs/SAEs/SADEs/device deficiencies/Protocol Deviations
- [REDACTED]
- [REDACTED]
- Cleansing of wound according to standard of care (record product applied)
- Photo of wound and upload to a digital [REDACTED]

Wound assessment

- [REDACTED]
- [REDACTED]
- [REDACTED]
- [REDACTED]
- [REDACTED]
- [REDACTED]
- Wound healed (yes/no)

Test Product assessment

- [REDACTED]
- [REDACTED]
- [REDACTED]
- Dressing application according to IFU
- Record applied additional wound care products (e.g., sec. dressing or barrier cream)

- Record any changes in concomitant medication
- Record if use of antibiotics and antiseptics since last visit
- Scheduling next Study visit V3 in the following week. Visit 3 must be 14 days after Visit 1 (+/-2 days) (Attention to compliance with maximum wear time of 7 days according to IFU)
- Perform device accountability
- Complete eCRF

Visit 3 Termination

- Insurance of subject's wellbeing. Review of AEs/ADEs/SAEs/SADEs/device deficiencies/Protocol Deviations
- [REDACTED]
- [REDACTED]
- Cleansing of wound according to standard of care (record product used)
- Photo of wound and upload to a digital [REDACTED]

Wound assessment

- [REDACTED]
- Wound healed (yes/no)

Test Product assessment

- [REDACTED]
- [REDACTED]
- [REDACTED]
- Record any changes in concomitant medication
- Record if use of antibiotics and antiseptics since last visit
- Handover to routine care
- Perform device accountability
- Complete eCRF

Termination visit wound healed

- Insurance of subject's wellbeing. Review of AEs/ADEs/SAEs/SADEs/device deficiencies/Protocol Deviations
- [REDACTED]
- [REDACTED]
- Cleansing of wound according to standard of care (if applicable) (record product used)
- Photo of wound and upload to a digital [REDACTED]

Wound assessment

- [REDACTED]
- Wound healed (yes/no)

Test Product assessment

- [REDACTED]
- [REDACTED]
- [REDACTED]
- Record any changes in concomitant medication

- Record if use of antibiotics and antiseptics since last visit
- Perform device accountability
- Complete eCRF

7.2. Dressing changes between study site visits.

The dressing should be replaced when wound care practice indicates that a change is needed, or when it has reached its maximum, but no more than 7 days. If the wound care practice indicates that a change is needed (strike through) more than the scheduled study visit once per week, additional visits at the site can be scheduled for dressing changes.

In the event of a completed dressing change between the weekly scheduled visits, it must be documented at the next scheduled weekly visit in the eCRF to capture the total number of dressings changes since last scheduled visit and numbers of test products used simultaneously per dressing change.

The subject will be instructed to complete a sheet for dressing changes, date of the event, and numbers of test products used simultaneously between the scheduled weekly site. Furthermore, the subject will be instructed to document any use of antiseptics, and reason for use if known, between the scheduled visits.

Dressing change can also take place at the subject's home by a homecare nurse.

The subject will be provided with additional test products at each visit for use at home in case of additional dressing changes in between visits. An information sheet for the homecare nurse will be distributed to the subjects to be shared with the homecare nurse, providing information about the study and the study treatment to ensure that the protocol is followed between scheduled visits.

No clinical investigation-related wound assessments are conducted during the additional visits and/or dressing changes at the subject's home. Cleansing of wound must be done according to standard of care if needed.

7.3. Unscheduled visits.

If circumstances demand it, e.g., due to specific issues with the test product or events which need to be assessed by the PI or delegate, an unscheduled visit may be scheduled. No clinical investigation-related wound assessments are conducted during the unscheduled visits.

7.4. Wound healed

If the wound is evaluated by PI or delegate to be healed before or at the termination visit 3 the subject must be terminated according to the termination Wound healed and not according to termination visit 3 as these assessments are not relevant when the wound has healed.

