7.5. Schedule of clinical-related procedures and assessments

Table 3. Chart showing the connection between visits and assessments.

	PER-FORMED BY	SCREENING VISIT	BASELINE VISIT	VISIT 2	TERMINATION VISIT WOUND HEALED	TERMINATION VISIT	UNS VISIT
VISIT	-	V0	V1	V2	-	V3	
WEEK	-	WEEK 0	WEEK 0	WEEK 1	-	WEEK 2	
DAY		DAY 0	DAY 0	DAY 7	-	DAY 14	

VISIT WINDOW	-	-	0-72 hours after injury	+/-2 days	-	+/-2 days	
GENERAL							
Introduction to the investigation and review of Patient Information Sheet/Informed Consent Form	Investigator or delegate	X	X				
Review of in- and exclusion criteria	Investigator or delegate	X					
Check and verification of in- and exclusion criteria	Investigator or delegate		X				
Informed Consent Signed	Investigator or delegate and Subject		X				
Enrollment in the investigation allocation of subject number	Investigator or delegate		X				
Collect Baseline information	Investigator or delegate		X				
Record concomitant medication	Investigator or delegate		X				
Review of AE/ADE/SAE/SADE/device deficiencies/Protocol Deviations	Investigator or delegate			X	X	X	X
Procedures/Assessments							
Cleansing of wound according to standard of care (record product used)	Investigator or delegate		X	X	X	X	X
Photo of wound and upload to a [REDACTED]	Investigator or delegate		X	X	X	X	
Wound area measurements using a digital [REDACTED]	Coloplast representative		X	X		X	
Wound healed (Yes/No)	Investigator or delegate			X	X	X	
[REDACTED]	Investigator or delegate		X	X		X	

[REDACTED]	Investigator or delegate			X	X	X	
[REDACTED]	Investigator or delegate		X	X		X	
[REDACTED]	Investigator or delegate		X	X		X	
[REDACTED]	Investigator or delegate		X	X		X	
[REDACTED]	Investigator or delegate		X	X		X	
[REDACTED]	Investigator or delegate			X	X	X	
[REDACTED]	Investigator or delegate		X	X	X	X	
Dressing application	Investigator or delegate		X	X			X
[REDACTED]	Investigator or delegate			X	X	X	
[REDACTED]	Investigator or delegate			X	X	X	
[REDACTED]	Investigator or delegate			X	X	X	
Record applied additional wound care products (e.g., sec. dressing or barrier cream)	Investigator or delegate		X	X			X
Record any changes in concomitant medication	Investigator or delegate			X	X	X	
Perform device accountability	Investigator or delegate		X	X	X	X	
Sheet for capture dressing changes and numbers of test products used simultaneously	Subject			X	X	X	

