10.2. Analysis of endpoints, individual questions, and assessments

All collected data including withdrawals will be accounted for in listings. All endpoints and baseline information will be listed and summarized by descriptive statistics. The summaries will be done in total and by the different population groups. Summaries and listing will include both safety/ITT and FAS population.

Summary statistics for continuous variables are presented with N, Mean, SD (standard deviation), Median, Min and Max, where N denotes the number of subjects contributing with non-missing data. For discrete variables, summary statistics are presented with N and percentage, where percentage is based on the total number of subjects/observations with non-missing data.

Other summaries and analyses can be made, if relevant.

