10.3. Analysis of primary endpoint

The primary endpoint proportion of wounds healed will be analyzed using a binomial proportion test.

The purpose of the primary analysis is to show non-inferiority to the performance of the similar product Aquacel Ag (a silver containing gelling fiber) on proportion of wounds healed, 77 %, with a non-inferiority margin of 20 %. (1)

Since the performance of Aquacel Ag is a fixed proportion, this is equivalent to testing whether the performance of Biatain Fiber Ag is superior to $77 - 20 = 57$ %.

Let the null hypothesis and the alternative hypothesis be defined as:

- $H_0: \mu_{\text{Biatain Fiber Ag}} \leq 57$ % wounds healed
- $H_1: \mu_{\text{Biatain Fiber Ag}} > 57$ % wounds healed

Where Non-inferiority will be demonstrated if H_0 is rejected.

This will be done using the proc freq procedure with a binomial test and if the lower limit of the 95 % confidence interval is above 57 % H_0 is rejected, and the success criteria fulfilled.

Furthermore, as a conservative estimate, a sensitivity analysis will be performed on the primary endpoint, where patients lost to follow-up, or otherwise missing information, will be considered not healed in regards to their wound.

The exploratory endpoints will be analysed descriptively and presented with confidence intervals.

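### As scheduled, any V3 wound-area summary would contain only unhealed wounds, because healed wounds bypass V3 and no area value is assigned to them

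*Combined protocol and SAP*

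**What the plan says.** Four parts of the combined protocol and SAP bear on this.

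- **Section 7.4.** Once a wound is judged healed, "the subject must be terminated according to the termination Wound healed and not according to termination visit 3". The reason given is that the V3 assessments are skipped "as these assessments are not relevant when the wound has healed".
- **Table 3 (section 7.5).** The row "Wound area measurements using a digital" (device name redacted) is marked at V1, V2 and V3 and is blank under the wound-healed termination. The row "Photo of wound and upload to a" (platform name redacted) is marked at all four, so an image of the healed wound is taken. V2 carries both an area mark and a healed yes/no item.
- **Section 10.2.** "All endpoints and baseline information will be listed and summarized by descriptive statistics". Continuous variables are presented with N, mean, SD, median and range, "where N denotes the number of subjects contributing with non-missing data".
- **Section 10.3.** The one missing-data rule covers the binary primary endpoint: "a sensitivity analysis will be performed on the primary endpoint, where patients lost to follow-up, or otherwise missing information, will be considered not healed". Exploratory endpoints are to be described with confidence intervals.

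The text of section 5.3, which lists the exploratory endpoints, is not readable. Sections 5.7 and 11 describe a dedicated photo and area-measurement system, so area is a working assessment in this study and not just a baseline descriptor.

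**The concern.** A healed wound has no V3 area because it healed. Whether a wound enters the V3 summary is therefore decided by the outcome, and the better the dressing performs, the fewer and the more selected the wounds that remain. This holds even if every judgement of healing is correct.

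A reader who sets mean area at V1 beside mean area at V3 would compare all wounds with the unhealed remainder. Remaining area would look too large and area reduction too small, and a confidence interval around either would describe unhealed wounds only. Section 2 says the study data will be compared with data on similar devices, so such a figure could be carried into that comparison.

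**Working it through.** **1. Reproduce the plan's sample size, which supplies the inputs.** Section 10.4 gives 44 completers and power 0.801 for a null of 57% (77% less a 20-point margin), an alternative of 77% and one-sided alpha 0.025.

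n = [(1.960 × √(0.57 × 0.43) + 0.842 × √(0.77 × 0.23)) / 0.20]² = 43.86, rounded up to 44. Power at 44 is 0.801. The plan's figure is reproduced. It is used below only to size the summary sets.

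**2. Size of the V3 area summary.** N at V3 = 44 × (1 − proportion healed by V3).

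| Proportion healed | Healed, no V3 area | In V3 area summary |
|---|---|---|
| 57% (null) | 25.1 | 18.9 |
| 77% (plan) | 33.9 | 10.1 |
| 90% (assumed) | 39.6 | 4.4 |

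If all 50 enrolled subjects were followed, the 77% row would give 50 × 0.23 = 11.5.

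**3. Effect on the mean.** The documents do not give the area left in unhealed wounds. Assume it averages r = 30% of baseline, range 10% to 50%. Healed means at least 95% reepithelialisation, so take h, the area left in a healed wound, between 0% and 5%. The summary as scheduled shows r. Over all wounds the mean is 0.23 × r + 0.77 × h.

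| r (mean as scheduled) | All wounds, h = 0% | All wounds, h = 5% |
|---|---|---|
| 10% | 2.3% | 6.2% |
| 30% | 6.9% | 10.8% |
| 50% | 11.5% | 15.4% |

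**4. V2.** The proportion healed before V2 is not given; assume 0% to 50%. The V2 summary then holds 44 × (1 − 0) = 44 down to 44 × (1 − 0.5) = 22 wounds. The share of these that go on to heal by V3 is (0.77 − 0) / (1 − 0) = 77% down to (0.77 − 0.5) / (1 − 0.5) = 54%. So the V2 set is wounds not yet healed, and most of them heal later.

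For a wound first found healed at V2, the V2 column of Table 3 calls for an area, while section 7.4 sends the subject to a termination that has none. The text does not say which governs.

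**The case against.** The strongest reply is that no biased analysis is shown to exist. The readable endpoints and assessments are percentage healed, antibiotic and antiseptic use, adverse events and device deficiencies. No readable section plans a mean change in area, and a hidden endpoint list could come with a hidden rule for healed wounds. This stands as a condition on the point. It does not remove it: area is scheduled after baseline, section 10.2 covers assessments as well as endpoints, and the readable part of section 10 gives healed wounds no area.

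Second, a photo is uploaded at the wound-healed termination, and section 11 has a designated person measure uploaded photos without limiting this to certain visits. One wound-assessment item at that termination is also redacted. An area might therefore be read in practice. But Table 3 does not schedule one, and even a measured value would belong to the termination visit and would not enter a V3 summary without a rule. The photo is best seen as part of the remedy.

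Third, N is printed with each summary, no test or success criterion uses area, and the error would run against the product. All of this is true and limits the importance of the point.

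A reader might also infer that the V2 summary describes only wounds that never heal. The documents do not support that: wounds open at V2 that heal later do have a scheduled V2 area. Nor does it follow that the area figures would contradict the primary result. Percentage healed and the area left in unhealed wounds are different quantities.

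**Conclusion.** The point holds for V3 and, in a weaker form, for V2. On the visible schedule, a V3 area summary would rest on about 10 of 44 completers, selected because they had not healed, and about 34 healed wounds would be absent. In illustration, it would show 30% of baseline area remaining, where the mean over all wounds would be 6.9% to 10.8%. The counts rest on the plan's 77% and 44; the percentages rest on an assumed residual area with no source in the documents. At V2 the summary omits only wounds healed before that visit, with those first found healed at V2 left ambiguous.

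The primary endpoint is binary, is recorded at the wound-healed termination, and is untouched. The point matters to the extent that post-baseline area or area change is summarised. It is a minor, easily repaired flaw in a descriptive analysis.

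**What to change.** Add to section 10.2:

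1. A wound recorded as healed enters the area and area-change summaries from the healed visit onward, including V3, and including V2 if first found healed there. Its value is either the area read from the termination photo or 0 cm2; choose one in advance.
2. If 0 cm2 is chosen, repeat the summary with healed wounds at 5% of baseline area, the most that the healed definition allows.
3. Report N per visit, split into measured and assigned or carried-forward values.
4. Show any unhealed-only summary separately and label it as such.

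The cost is a few lines of text and programming, with no new visits or subjects. Reading the termination photos would add about 34 area measurements on images already taken. The downside is that about 77% of V3 values would be assigned or carried forward, so the all-wound summary would partly restate the primary endpoint; with healed wounds at 0 and more than half healed, its median would be 0. Showing both summaries, each labelled, deals with this.

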7.5. Schedule of clinical-related procedures and assessments

Table 3. Chart showing the connection between visits and assessments.

	PER-FORMED BY	SCREENING VISIT	BASELINE VISIT	VISIT 2	TERMINATION VISIT WOUND HEALED	TERMINATION VISIT	UNS VISIT
VISIT	-	V0	V1	V2	-	V3	
WEEK	-	WEEK 0	WEEK 0	WEEK 1	-	WEEK 2	
DAY		DAY 0	DAY 0	DAY 7	-	DAY 14	

VISIT WINDOW	-	-	0-72 hours after injury	+/-2 days	-	+/-2 days	
GENERAL							
Introduction to the investigation and review of Patient Information Sheet/Informed Consent Form	Investigator or delegate	X	X				
Review of in- and exclusion criteria	Investigator or delegate	X					
Check and verification of in- and exclusion criteria	Investigator or delegate		X				
Informed Consent Signed	Investigator or delegate and Subject		X				
Enrollment in the investigation allocation of subject number	Investigator or delegate		X				
Collect Baseline information	Investigator or delegate		X				
Record concomitant medication	Investigator or delegate		X				
Review of AE/ADE/SAE/SADE/device deficiencies/Protocol Deviations	Investigator or delegate			X	X	X	X
Procedures/Assessments							
Cleansing of wound according to standard of care (record product used)	Investigator or delegate		X	X	X	X	X
Photo of wound and upload to a [REDACTED]	Investigator or delegate		X	X	X	X	
Wound area measurements using a digital [REDACTED]	Coloplast representative		X	X		X	
Wound healed (Yes/No)	Investigator or delegate			X	X	X	
[REDACTED]	Investigator or delegate		X	X		X	

[REDACTED]	Investigator or delegate			X	X	X	
[REDACTED]	Investigator or delegate		X	X		X	
[REDACTED]	Investigator or delegate		X	X		X	
[REDACTED]	Investigator or delegate		X	X		X	
[REDACTED]	Investigator or delegate		X	X		X	
[REDACTED]	Investigator or delegate			X	X	X	
[REDACTED]	Investigator or delegate		X	X	X	X	
Dressing application	Investigator or delegate		X	X			X
[REDACTED]	Investigator or delegate			X	X	X	
[REDACTED]	Investigator or delegate			X	X	X	
[REDACTED]	Investigator or delegate			X	X	X	
Record applied additional wound care products (e.g., sec. dressing or barrier cream)	Investigator or delegate		X	X			X
Record any changes in concomitant medication	Investigator or delegate			X	X	X	
Perform device accountability	Investigator or delegate		X	X	X	X	
Sheet for capture dressing changes and numbers of test products used simultaneously	Subject			X	X	X	
Instruction to the subject (including sheet for dressing changes and numbers of test products used simultaneously)	Investigator or delegate		X				

Handover to routine care	Investigator or delegate					X	
Complete eCRF	Investigator or delegate		X	X	X	X	X
Schedule Baseline Visit 1	Investigator or delegate	X					
Schedule Visit 2	Investigator or delegate		X				
Schedule Termination Visit V3	Investigator or delegate			X			
ADDITIONAL ASSESSMENTS							
Use of antibiotics and anti-septics since last visit	Investigator or delegate			X	X	X	

7.6. Concomitant treatment

Only concomitant medication/treatment that can impact wound healing should be registered. These include NSAID, glucocorticoid steroids and chemotherapeutic drugs. If subject use antibiotics or antiseptics after baseline V1, this must be documented in the eCRF with description on reason for use and which treatment used.

7.7. Supplementary materials and equipment

The Sponsor will provide the Principal Investigators with supplementary materials for the investigation such as computers with access to eCRF if needed and phones with the [REDACTED] installed to obtain photos.

8. Risk – benefit analysis and ethical considerations

8.1. Risk-benefit analysis of the investigational device

A risk analysis according to ISO 14971 Application of risk management to medical devices has been conducted. Risks have been proven minimized or eliminated through appropriate design control, confirmed by pre-clinical bench and laboratory testing.

All unacceptable risks related to the device have been mitigated as far as possible and have been deemed acceptable for the clinical study.

